#### 8.4.3. Exploratory Analyses

Company Confidential Information

[figure not shown]
• Company Confidential Information

- Company Confidential Information

- 

Company Confidential Information

## **8.5. Safety Analyses**

All safety assessments, including adverse event, clinical laboratory and vital sign data will be summarized with descriptive statistics, where appropriate, and presented in the data listings.

### **8.5.1. Extent of Exposure**

Below by-subject listing will be provided:

- Initial study treatment dosing, including initial treatment, dosage, frequency, time of administration, and ongoing etc. information.
- Study treatment adjustment, including adjustment start/end date, type, action taken, dosage, frequency, unit, primary reason for action taken, AE/ADR name (if available).

### **8.5.2. Adverse Events**

An AE is defined as any untoward medical occurrence in a patient enrolled into this study regardless of its causal relationship to treatment.

An ADR is defined as any response to a medicinal product that is noxious and unintended and that occurs at doses normally used in humans for the prophylaxis, diagnosis, or therapy of diseases or for the restoration, correction, or modification of physiological function. Response in this context means that a causal relationship between a medicinal product and an AE is at least a reasonable possibility. Adverse reaction also includes adverse clinical consequences associated with use of the product outside the terms of the Summary of Product Characteristics or other conditions laid down for the marketing and use of the product (including prescribed doses higher than those recommended, overdoses, or abuse).

An SAE is defined as any untoward medical occurrence that, at any dose:

1. Results in DEATH.
2. Is immediately LIFE THREATENING? The term “life threatening” refers to an event in which the subject was at risk of death at the time of the event; it does not refer to an event that hypothetically might have caused death if it were more severe.
3. Requires inpatient HOSPITALIZATION or prolongation of existing hospitalization.
4. Results in persistent or significant DISABILITY/INCAPACITY.
5. Is a CONGENITAL ANOMALY/BIRTH DEFECT.
6. Is an IMPORTANT MEDICAL EVENT that satisfies any of the following:
  - a. May require intervention to prevent items 1 through 5 above.
  - b. May expose the subject to danger, even though the event is not immediately life threatening or fatal or does not result in hospitalization.
  - c. Includes any event or synonym described in the Takeda Medically Significant AE List (Table 8-1).

**Table 8-1 Takeda Medically Significant AE List**

Term	
Acute respiratory failure/Acute respiratory distress syndrome (ARDS)	Hepatic necrosis
Torsade de pointes/Ventricular fibrillation/Ventricular tachycardia	Acute liver failure
Malignant hypertension	Anaphylactic shock
Convulsive seizure	Acute renal failure
Agranulocytosis	Pulmonary hypertension
Aplastic anaemia	Pulmonary fibrosis
Toxic epidermal necrolysis/Stevens-Johnson syndrome	Neuroleptic malignant syndrome/Malignant hyperthermia Spontaneous abortion/stillbirth and fetal death Confirmed or suspected transmission of infection agent by a medicinal product Confirmed or suspected endotoxin shock

The following AEs will be considered AESIs: pancreatitis, hepatic disorders, and hypersensitivity reactions (including angioedema, anaphylaxis, and Stevens-Johnson syndrome). Targeted follow-up forms have been developed to further guide the collection of data of AESIs and the forms need to be submitted to the sponsor as part of the AE source documents.

Summaries of below adverse events will be provided by System Organ Class (SOC) and preferred term by treatment using the Medical Dictionary for Regulatory Activities (MedDRA) using absolute frequencies and percentages as well as 95% confidence intervals:

- Overview of all adverse events: consist of total number of AEs, total number of patients with AEs and the number of AEs requiring discontinuation.
- The incidence and severity of all adverse events will be summarized by body system.
- Adverse events leading to treatment discontinuation.
- Adverse drug reactions
- SAEs
- Serious adverse drug reactions
- AESIs

The summary tables will be displayed alphabetically within system organ class. If a subject reports more than one condition that is coded to the same system organ class or preferred term, the subject will be counted only once at that level.

The following listings will also be generated: a listing of all adverse events with severity and causality information, listing of leading to study drug discontinuation, a listing of adverse drug reactions, a listing of serious adverse events, a listing of serious adverse drug reactions and a listing of adverse event of special interest.

### **8.5.3. Clinical Laboratory Evaluations**

A by-subject listing of baseline values, the values at each visit, and changes from baseline values in the clinical laboratory measurements will be provided. The clinical significance of laboratory abnormalities based on investigator's judgment will be flagged.

### **8.5.4. Vital Signs**

Vital sign data will include systolic and diastolic blood pressure. If multiple vital sign data are available, then the assessment closest to the visit time point will be used.

Vital sign data (including baseline, absolute and change from baseline values) will be summarized by treatment using descriptive statistics. A by-subject listing of baseline values, the values at each visit, and changes from baseline values in the vital signs measurements will be provided.

## **8.6. Other Analyses**

### **8.6.1. Country Related Analyses**

Indication information (alogliptin and alogliptin FDCs market status, T2DM standard of care) will be summarized with categorical statistics, and presented in the data listing.

### **8.6.2. Physician Related Analyses**

Prescribing physician-relevant information (general/specialized practitioner) will be summarized with categorical statistics, and presented in the data listing.

## **9. Impact on Analysis Due to Study Termination**

Due to Takeda's decision, Alogliptin 5009 study need to be early-terminated. The impact will include below three aspects:

### **9.1. Actual Sample Size**

By the study early-termination, the actual sample size enrolled is far less than planned, which can not reach to the worst-case scenario of half-width 0.05. If the sample primary endpoint

standard deviation is the same as expected one (0.65), the actual sample size will lead to the reduction of analysis precision and the broadening of half-width.

## **9.2. Impact on Analyses**

For the analyses results, study termination will have no impact on the point estimation, but the confidence interval range will be broadend.

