4.2.1 Reasons for Withdrawal

This study does not require administration of any investigational product and therefore does not require any stopping criteria.

The reasons for patients not completing the study will be recorded. A patient may be withdrawn from the study for any of the following reasons:

1. The patient does not meet the protocol inclusion/exclusion criteria.
2. The patient withdraws consent or the investigator or Takeda decides to discontinue the patient's participation in the study.

The investigator will also withdraw a patient if Takeda terminates the study.

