6.2.2 Eliciting and Documenting Adverse Events

Adverse drug reactions, AESIs, and SAEs will be assessed from the time the patient signs the ICF until the end of study participation. Any AE volunteered by the patient will also be recorded.

The investigator is responsible for following SAEs and AESIs until resolution, until the patient returns to baseline status, or until the condition has stabilized with the expectation that it will remain chronic, even if this extends beyond study participation.

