## 3. STUDY DESIGN

This is an observational, prospective, multicenter study in adult patients with T2DM diagnosis who have made the decision, along with their treating physician, to begin treatment with alogliptin or alogliptin FDCs.

The purpose of this study is to observe alogliptin and alogliptin FDCs utilization patterns, as well as clinical response to treatment with alogliptin or alogliptin FDCs, in standard clinical practice. No investigational product will be administered in this study.

The observational study will include approximate 1142 patients with T2DM treated with alogliptin or alogliptin FDCs in approximately 40 sites.

The planned maximum duration of this study per patient will be 6 months or up to loss to follow-up or death, whichever occurs first. In this study, Patients will attend a baseline visit followed by visits approximately at Month 3 and 6. Patients will not be asked to travel to the site only for the purpose of this study; the study visits will be performed during regular doctor's appointments.

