## 7. ANALYSIS POPULATION

### 7.1. Analysis Sets

The analysis will be performed on the complete set of patients enrolled in the study. Subgroup analyses will be carried out on the subgroups defined in Section 4.3.

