## **9.3. Impact of Limited Visit**

The study termination will lead to missing visit of V2 or V3, and efficacy results might not be obvious.

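### SAP 9.2 says early termination leaves point estimates unchanged, which is wrong for crude once-per-subject adverse event percentages on a denominator fixed at enrolment

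*SAP*

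**What the plan says.** SAP Section 9 was written once the sponsor had decided to stop the study. Section 9.1 says enrolment fell far short of plan and precision will suffer. Section 9.2 then states: "For the analyses results, study termination will have no impact on the point estimation, but the confidence interval range will be broadend". Section 9.3 adds: "The study termination will lead to missing visit of V2 or V3, and efficacy results might not be obvious". The only consequence it draws from the missing visits concerns efficacy.

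The rules that determine the safety percentages are elsewhere:

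- Protocol 4.2.1, on termination: "The investigator will also withdraw a patient if Takeda terminates the study".
- Protocol 6.2.2, on the assessment window: "Adverse drug reactions, AESIs, and SAEs will be assessed from the time the patient signs the ICF until the end of study participation".
- SAP 3, on planned follow-up: "The planned maximum duration of this study per patient will be 6 months or up to loss to follow-up or death, whichever occurs first".
- SAP 7.1, on the analysis set: "The analysis will be performed on the complete set of patients enrolled in the study".
- SAP 8.5.2, on a patient with repeated events in the same class or term: "the subject will be counted only once at that level". The summaries are counts and percentages with 95% confidence intervals.
- SAP 8.2.1: missing data are not imputed.
- SAP 8.5.1, on exposure: "Below by-subject listing will be provided". No readable section summarises follow-up or exposure time.

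**The concern.** Termination does two things here. It reduces the number of patients, and it shortens follow-up for those already enrolled. Section 9.2 fits the first: fewer patients means wider intervals around an estimate that need not shift. It overlooks the second. A cumulative percentage depends on how long each patient is watched, so shorter follow-up changes what it estimates as well as its precision.

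Safety is a stated secondary objective. In a descriptive study without formal testing, the percentages are themselves the result. A reader relying on 9.2 would take the AE, ADR, SAE and AESI percentages as those of a six-month study with somewhat wider intervals, and no planned summary table would show how much follow-up lay behind them.

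**Working it through.** **The plan's own figures.** SAP 6 uses SD 0.65 and correlation 0.35, so the SD of the paired difference is 0.65 × √(2 × (1 − 0.35)) = 0.741. The exact paired-mean interval calculation gives 899 pairs for half-width 0.05 (conditional probability 0.904), and 899 / 0.75 = 1198.7, rounded up to 1199. Both match the plan. With fewer pairs the interval widens as 9.1 and 9.2 say: at an assumed 200 pairs the expected half-width is about 1.96 × 0.741 / √200 = 0.103. That part of Section 9 stands.

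**Direction for safety percentages.** For patient *i*, let T be the time of the first event of a given kind and C the follow-up time. The crude percentage is the number of patients with T ≤ C, divided by the number enrolled. Shortening C for the same patients can turn a counted event into an uncounted one, never the reverse, and the denominator does not move. The percentage therefore falls or stays the same. It stays the same only if no first event lies in the lost time. In 2,000 simulated data sets, truncating the same patients never raised it (maximum increase 0.0).

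**Size, under assumptions.** The documents do not give the share of patients cut, when they were cut, or event rates. Write p for the 6-month risk, L = −ln(1 − p), u for time as a fraction of 6 months, and F(u) = 1 − exp(−L·u^k). Here k = 1 is constant hazard, k = 0.5 has early events and k = 1.5 late events. If a share q is cut uniformly over 0 to 6 months:

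reported = (1 − q)·p + q·∫F(u)du, and for k = 1 the integral is 1 − p/L.

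- p = 0.20, q = 0.5: L = 0.22314; integral = 1 − 0.20/0.22314 = 0.1037; reported = 0.5 × 0.20 + 0.5 × 0.1037 = 0.152.
- p = 0.02, q = 0.5: L = 0.0202027; integral = 1 − 0.02/0.0202027 = 0.0100; reported = 0.5 × 0.02 + 0.5 × 0.0100 = 0.015.

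If instead a share q is cut at Month 3, so that only V3 is missed, reported = (1 − q)·p + q·F(0.5).

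| Assumed case | True 6-month risk | Reported, k = 1 | k = 0.5 | k = 1.5 |
|---|---|---|---|---|
| Half cut, uniform over 0–6 months | 20% | 15.2% | 16.9% | 14.2% |
| Half cut, uniform over 0–6 months | 2% | 1.5% | – | – |
| Half cut at Month 3 | 20% | 15.3% | 17.3% | 13.8% |
| Half cut at Month 3 | 10% | 7.6% | 8.6% | – |
| Half cut at Month 3 | 5% | 3.8% | 4.3% | – |

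**Against the plan's own 25% dropout.** Ordinary dropout already lowers these percentages, so the fair comparator includes it. With 25% dropout uniform over 6 months and independent of termination, reported = ∫f(u)(1 − 0.25u)(1 − q·u)du, where f is the event-time density. For p = 0.20:

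| Share cut by termination | k = 1 | k = 0.5 | k = 1.5 |
|---|---|---|---|
| 0 | 17.6% | 18.4% | 17.1% |
| 25% | 15.6% | 17.1% | 14.7% |
| 50% | 13.6% | 15.7% | 12.3% |

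**Would a person-time rate help?** In a simulation of 1,000,000 patients with p = 0.20 and constant hazard (true rate 0.22314 / 0.5 year = 0.446 per patient-year), uniform cutting of 25%, 50% and 100% of patients gave crude percentages of 17.6%, 15.2% and 10.4%. The rates were 0.446, 0.446 and 0.447. The rate is stable because the hazard is constant, which is the assumption to state beside it. All cases assume truncation unrelated to outcome.

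**The case against.** The strongest reply is that 9.2 is commentary. It changes no output, the study is descriptive, and neither document names a six-month cumulative risk as the safety estimand. Withdrawals by reason (SAP 8.3.1) and dosing listings (8.5.1) are planned, so an attentive reader could see that follow-up was cut. Part of this stands: the defect lies in interpretation and leaves the primary analysis alone, and patient-year rates are one reasonable remedy among several. But 9.2 makes a categorical statement about all results, and withdrawals by reason do not show how long patients were followed.

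Stronger readings are tempting but not supported:

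- *Every safety percentage must fall.* SAP 8.5.2 also summarises severity. If each patient is classified by worst grade, which the SAP does not say, losing a later severe event can raise a milder category. Protocol 7.8.2 places safety analyses on a safety population that neither document defines; if it excludes patients without post-baseline data, the direction is open. SAP 8.5.2 summaries are also by treatment, and the SAP does not say how switchers are assigned.
- *Nothing is known about patients cut before Month 3.* Table 12-1 schedules the safety report at Months 3 and 6, but events are assessed from consent (Protocol 6.2.2), must be reported promptly once the site knows of them (6.2.3), and may be taken from medical records (Table 12-1, footnote 4). If half of patients are cut, half of those at Month 3 and half uniformly before it with events captured to the cut, a 20% risk is reported as 14.0% under constant hazard.
- *Later events disappear altogether.* Protocol 7.8.2 provides that AEs reported directly to authorities or to the sponsor's drug safety unit, outside the study database, are listed or tabulated in the final report. Nothing places them in the 8.5.2 percentages.
- *A smaller sample must show fewer events.* Chance or case mix can move the percentage either way. The result above compares the same patients under shorter and full planned follow-up.
- *Omitting Kaplan-Meier for time to dose change is part of the error.* The protocol abstract makes it optional, Protocol 7.8.2 itself prescribes percentages for dose change, and SAP 8.4.3 is redacted.

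**Conclusion.** The concern holds for crude once-per-subject any-event, system organ class and preferred term percentages of AEs, ADRs, SAEs and AESIs on a denominator fixed at enrolment, such as the all-enrolled set of SAP 7.1. For these, the statement in 9.2 is wrong as written. The direction follows from the plan's own rules: the percentages are at or below what full planned follow-up of the same patients would have given.

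The size is unknown. In the uniform half-cut illustration the relative loss is about a quarter, (20 − 15.2)/20 = 24%. In absolute terms that is about 5 points at an assumed 20% risk and 0.5 points at 2%, and it depends on how many patients were cut, when, and when events occur.

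A reader might infer that 9.2 also fails for the primary endpoint. The documents do not show that: mean HbA1c change at V3 keeps its target if truncation is unrelated to outcome, and a sponsor's decision to stop is compatible with that assumption though no proof of it. This should be fixed. It affects the reading of a secondary objective and leaves the primary result unchallenged.

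**What to change.** 1. In SAP 9.2, limit the statement about unchanged point estimates to the effect of reduced N and to mean HbA1c change when truncation is unrelated to outcome. State in 9.2 or 9.3 that cumulative safety percentages are understated relative to full planned follow-up.
2. In SAP 8.5.1, add a summary of follow-up time and exposure time.
3. In SAP 8.5.2, add AE, ADR, SAE and AESI rates per patient-year beside the crude percentages. State that they assume a roughly constant hazard, and define time at risk: on treatment or in study, and from which start. Protocol 7.8 uses the first day on alogliptin as study entry, whereas 4.2 counts from consent. State the denominator too, including how switchers are handled in by-treatment summaries.

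The cost is a few sentences and a few standard tables. Treatment start and end dates (Protocol 6.1.5) and event onset times (6.2.3) are already collected. The documents do not show whether a termination or last-contact date was recorded; failing that, the last study visit, which ends study duration under Protocol 4.2, can serve as the end of follow-up.

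Optional: a Kaplan-Meier or cumulative incidence estimate for time to dose escalation or reduction, which the protocol abstract permits.

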## **9.3. Impact of Limited Visit**

The study termination will lead to missing visit of V2 or V3, and efficacy results might not be obvious.

